In addition, a structured questionnaire will be used to obtain the estimated: i) time and material cost of installing the tool (feasibility) during installation, ii) perceived adverse effects after one month of installation, and iii) community acceptance of ITENs with ITWS. The physical durability of the intervention will be evaluated through physical inspection of the ITENs and ITWS for the continued presence and fabric integrity. Chemical durability will be assessed using samples of netting that will be evaluated for bioefficacy using laboratory reared populations of pyrethroid resistant *An. arabiensis*, *Culex quinquefasciatus*, *An. funestus* as well as pyrethroid susceptible *Aedes aegypti* mosquitoes, followed by chemical testing according to standard WHO guidelines and procedures (10). In addition, the perception, use and practice of the tool will be examined through Focus Group Discussions.

1 **Methods: Participants, interventions and outcomes**

2 **Study setting {9}**

3 The trial will be implemented in the villages of Pongwe, Madesa and Mazizi in Chalinze district
4 located in coastal Tanzania. The average rainfall is 1200 to 2100 mm per year and the average
5 temperature is approximately 28°C in the region. The region has two rainfall seasons yearly: the
6 long rainfall from March to May and short rainfall from November to December. The main
7 occupation for majority of the residents in villages of Chalinze is farming. The population of the
8 study area was 13,740 while the average household size in the district was 4.5 (11). The malaria
9 prevalence by PCR in the study area was more than 40% in the survey designed to assess
10 gametocyte in children of age 7 years old and above ([name]. *pers comm.*). More than sixty
11 percent of houses had window screens and thirteen percent had closed eaves in a study conducted
12 previously in the study area (11). An estimated 1800 people based on the average household size
13 and number of households will be tested for malaria at each survey, thus, nine hundred people per
14 arm will be screened for malaria.

15

16 **Eligibility criteria {10}**

17 Recruitment for the will be by household. To be eligible, residents must live in a house with strong
18 (intact) walls, having open eaves and unscreened windows. Residents of study houses who are
19 over the age of 6 months will be eligible for the follow up surveys.

20

21 **Eligibility criteria for individuals who will perform the interventions**

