50 ul blood from members of above 6 months old					X	X		
Density of malaria vectors and Nuisance mosquitoes					X	X		
Feasibility Cost		X						
Longevity, fabric integrity, community acceptance and practice.				X		X		
Bioefficacy & Chemical retainment						X		

2

3

4 **Sample size {14}**

5 With 225 houses per arm was an assumed 4.5 residents per household (14), then if prevalence in
6 the control arm is 20% the study would have 90% power to detect a relative reduction of 30% to a
7 prevalence of 14% assuming a conservative between-house coefficient of variation of 0.5.

1

2 **Recruitment {15}**

3 Once permission from the District Medical Officer and village heads is obtained, meetings with
4 the village leaders will be convened to discuss the aim and procedures of the trial, and to select the
5 villages where houses that meet eligibility criteria can be found. Once villages are selected,
6 community sensitization will be conducted among all the selected villages to provide information
7 on the purpose of the study to the people, including the adverse consequences of vector-borne
8 diseases, the benefits and risks of using ITENS and ITWS, and caring for the intervention. This
9 will be followed by recruitment of the households through door-to-door process, facilitated by
10 community leaders as key informants to introduce field teams to households.

11

12 **Assignment of interventions: allocation**

13 **Sequence generation {16a}**

14 Household identification numbers stratified by sub-village will be provided to a statistician that
15 will not be in the field during the community enrolment. Simple randomization within blocks of
16 sub-villages to randomly allocate households between two arms will be conducted. Randomization
17 of all study households will be done simultaneously.

18

19 **Concealment mechanism {16b}**

20 This trial will not have continuous recruitment. All households will be recruited at the start of the
21 study and randomized simultaneously.

1

2 **Implementation {16c}**

3 After enrollment of all households by trained field workers, the trial statisticians will generate
4 allocation sequence and assign households to interventions through randomization stratified by
5 sub-village.

6

7 **Assignment of interventions: Blinding**

8 **Who will be blinded {17a}**

9 This is an open label trial because intervention can be visually observed.

10

11 **Procedure for unblinding if needed {17b}**

12 Not Applicable.

13

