9 quantitative polymerase chain reaction (qPCR) analysis. Point of care diagnosis for febrile
10 individuals will be SD Bioline Malaria Ag Pf/Pan rapid diagnostic test (RDT) as per Tanzanian
11 guidelines (13).

12 Used RDT kits will be stored in a locked shipping container at IHI until the data is completed and
13 locked, then the samples will be destroyed on-site in the Clinical Trials facility Incinerator.

14

15 **Statistical methods**

16 **Statistical methods for primary and secondary outcomes {20a}**

17 The primary endpoint which is detection of malaria parasitemia through qPCR after the long rainy
18 season (June/July 2022) will be analysed using mixed effects binary logistic regression, with a
19 random effect for household to account for clustering. Analysis of secondary endpoints malaria
20 parasitemia will be tested using qPCR after the short rainy season (January/February 2022) as well

1 as clinical malaria cases and malaria prevalence shortly after the short rainy season and long rainy
2 will also be analysed following the same approach.

3 Negative binomial mixed effect model will be performed for mosquito density data, with random
4 effect for household.

5 The baseline characteristics collected during the survey, including age, sex, education, number of
6 participants, household size, occupation, sleeping spaces, nets per house, nature of houses (wall,
7 roof, and floor), community acceptance of LLINs (use rate and any side effects) and
8 socioeconomic quintiles will be presented by arm.

9 Principal component analysis (PCA) will be carried out to determine a combination of variables
10 for socioeconomic status to explain the overall observed variation and reduce the complexity of
11 the data, by calculating a weighted score for the socioeconomic status of each household of the
12 population and divided into five quintiles: lowest, low, middle, high and highest.

13 Proportion of the outcomes (attrition, fabric integrity and community acceptance) will be presented
14 in percentages.

15 Recorded information during the FGD will be transcribed and grouped into different themes based
16 on inductive thematic analysis of interview summaries. Reports will be illustrated with verbatim
17 quotes of themes and sub-themes identified.

18

19 **Interim analyses {21b}**

20 No interim analyses will be carried out.

21

1 **Methods for additional analyses (e.g. subgroup analyses) {20b}**

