2 An analysis of the intervention effect within subgroups defined by age (under 5s, aged 5-15, and
3 aged 16 or over), socioeconomic status, gender, among others will be carried out on malaria
4 prevalence at both surveys using the same methods as for the primary endpoint.

5

6 **Methods in analysis to handle protocol non-adherence and any statistical methods to handle**
7 **missing data {20c}**

8 Minimal protocol non-adherence is expected because of the nature of the intervention, however
9 we will carry out an intention to treat in which households are analysed according to allocation
10 regardless of whether the intervention was adhered to. A secondary per protocol analysis which
11 excludes houses that removed the intervention will be carried out. At an individual level,
12 participants who report being away from home for more than a week during the fortnight preceding
13 testing will be excluded from the primary analysis but included in a secondary analysis. We expect
14 there to be minimal missing data on the primary endpoint, in which case complete case analysis
15 will be used. If there is more missing data than expected, a secondary analysis in which multiple
16 imputation is applied under the assumption of missing at random will be carried out.

17

18 **Plans to give access to the full protocol, participant level-data and statistical code {31c}**

19 Full protocol, statistical analysis plan, anonymized level-data and statistical code will be made
20 available on reasonable request.

21

1 **Oversight and monitoring**

2 **Composition of the coordinating centre and trial steering committee {5d}**

3 The Ifakara Health Institute is the trial sponsor and coordinating centre. Study investigators meet
4 weekly to review trial progress. A trial steering committee consisting of study investigators and
5 independent experts will meet after every study survey.

6

7 **Composition of the data monitoring committee, its role and reporting structure {21a}**

8 Although we don't anticipate any safety issues in this trial since the intervention is similar to LLINs
9 which are used extensively in malaria endemic regions a data monitoring committee has been
10 appointed. The committee is composed of a clinician, an entomologist and a statistician, is
11 independent of the trial sponsor and funder, and has no competing interests. The committee will
12 meet after the data from each survey have been collected. The committee will consider safety data

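### The primary model in {20a} is stated without covariates: naming age group and sex, and socioeconomic status if recorded at enrolment, is a nearly free gain that may be nil and is at most about 4 power points

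*Protocol*

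**What the plan says.** Under the statistical methods heading ({20a}), the primary endpoint after the long rainy "season (June/July 2022) will be analysed using mixed effects binary logistic regression, with a" "random effect for household to account for clustering". The January/February qPCR endpoint follows the same approach. No fixed effect other than arm is mentioned, and nothing says that adjustment is excluded.

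The same section lists what is recorded: "The baseline characteristics collected during the survey, including age, sex, education, number of" residents and other household items. It ends with the statement that "socioeconomic quintiles will be presented by arm". Section {20b} gives these variables a second use: "An analysis of the intervention effect within subgroups defined by age (under 5s, aged 5-15, and" 16 or over), and by socioeconomic status and gender, for malaria "prevalence at both surveys using the same methods as for the primary endpoint".

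The participant timeline ({13}) puts baseline data at enrolment in May, installation in June 2021, and blood sampling only in January and June 2022. Section {31c} mentions a separate statistical analysis plan, which is not at hand.

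**The concern.** Adjusting for a prognostic variable that the intervention cannot change normally raises power in a logistic model. It also keeps a chance difference in that variable from entering the effect estimate. Three features make the question relevant here.

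- There is no baseline blood sample, so adjustment for earlier parasitaemia is impossible. Age, sex and socioeconomic status are the obvious prognostic candidates left.
- Residents are eligible from 6 months upwards with no upper limit, and randomisation is stratified by sub-village only.
- The design has little slack. {14} uses 4.5 residents per house, while {9} expects 1800 people tested in 450 houses, which is 1800/450 = 4.0.

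At stake is a modest amount of power on the primary endpoint. The validity of the trial is not in question. Whether the sub-village stratifier belongs in the model is a separate matter and is not counted here.

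**Working it through.** **1. The stated power.** Inputs from {14}: "With 225 houses per arm was an assumed 4.5 residents per household (14), then if prevalence in" controls is 20%, falling to 14%, with between-house coefficient of variation k = 0.5. Two-sided alpha of 0.05 is assumed, since none is stated. The unmatched cluster-trial formula (Hayes-Bennett) is

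c = 1 + (z_a + z_b)² · V / (p0 − p1)², with V = p0(1−p0)/m + p1(1−p1)/m + k²(p0² + p1²).

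- V = 0.16/4.5 + 0.1204/4.5 + 0.25 × (0.04 + 0.0196) = 0.0356 + 0.0268 + 0.0149 = 0.0772.
- c = 1 + (1.960 + 1.282)² × 0.0772/0.0036 = 226.4 houses per arm, against 225 stated.
- Power at 225: Φ(√(224 × 0.0036/0.0772) − 1.96) = 89.8%, or 90.0% without the −1 correction.
- Cross-check: ICC = k²p0/(1−p0) = 0.25 × 0.2/0.8 = 0.0625, design effect 1 + 3.5 × 0.0625 = 1.22, power 90.3%.

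The stated 90% reproduces with no covariate. At 4.0 residents per house the same formula gives 86.9%.

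**2. Adjustment, by formula.** Let covariates explain a share r_w of the first two terms of V and r_b of the third: V = 0.0623(1 − r_w) + 0.0149(1 − r_b). The shares are assumptions.

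| r_w | r_b | Power | Houses per arm for 90% |
|---|---|---|---|
| 0 | 0 | 89.8% | 226 |
| 2% | 0 | 90.3% | 223 |
| 5% | 10% | 91.5% | 213 |
| 10% | 30% | 93.6% | 195 |

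**3. Adjustment, by simulation.** 450 houses with mean 4.5 residents, control prevalence 20% and intervention 14%, and a random-intercept logistic model fitted with and without age group, sex and a linear socioeconomic score; 800 trials per scenario. The assumed age mix is 16/28/56% for under 5, 5-15 and 16 or over. The residual house effect was reduced as covariate effects grew, to keep total clustering roughly at k = 0.5.

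| Assumed association (OR for age 5-15; per quintile; sex) | Power, unadjusted to adjusted | log OR | SE of log OR |
|---|---|---|---|
| None | 90.9% to 90.6% | −0.472 to −0.473 | 0.1443 to 0.1446 |
| Weak (1.5; 0.86; 1.1) | 90.5% to 90.9% | −0.472 to −0.476 | 0.1434 to 0.1425 |
| Moderate (2.2; 0.74; 1.2) | 89.4% to 91.4% | −0.462 to −0.471 | 0.1422 to 0.1381 |
| Strong (3.3; 0.67; 1.35) | 90.7% to 95.1% | −0.457 to −0.485 | 0.1408 to 0.1350 |

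Each power figure has a simulation error of about √(0.9 × 0.1/800) = 1.1 points, but each pair uses the same data sets. A separate set of 300 trials per scenario gave changes of −0.3, +1.7, +2.7 and +3.4 points.

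**4. Age group alone.** A second simulation (250 trials per scenario) used an assumed age mix of 16/30/54%. The squared ratio of mean Wald z, adjusted to unadjusted, was 1.00 with no age pattern, 1.025 with prevalences of 12/30/17%, and 1.085 with 15/40/10%. In the last case power went from about 88.8% to 91.1%. The upper end of the range in step 3 therefore depends on socioeconomic status being usable.

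**5. Chance imbalance.** With 225 × 4.5 = 1012.5 people per arm and 30% aged 5-15, the SE of the between-arm difference in that share is √(2 × 0.3 × 0.7/1012.5) = 2.0 points, ignoring clustering of age within houses. Under the 15/40/10% pattern the other ages average (16 × 15 + 54 × 10)/70 = 11.1%. One SE of imbalance then shifts prevalence by 0.020 × (40 − 11.1) = 0.6 points, against a target difference of 6 points.

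**The case against.** The strongest reply is that a covariate list is commonly left to the analysis plan. One is mentioned in {31c}, and silence in the Protocol does not prove an unadjusted analysis. That stands as a limit on the wording: the Protocol does not exclude adjustment. It does not remove the point, because {20a} itself sets out the primary model and says what the collected variables are for.

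Second, nothing needs repair: the unadjusted analysis is valid and its power claim reproduces. This stands in full.

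Third, the size rests on invented inputs. It does, because the Protocol gives no age mix, no prevalence by age and no socioeconomic gradient. Only a range starting at zero can be defended. Part of the gain in z also comes from the conditional odds ratio moving away from 1, so the gain is better described as power than as precision.

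Fourth, imbalance large enough to mislead is unlikely. Step 5 agrees, and the confidence interval already allows for such chance variation.

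Fifth, the change is not wholly free. {20a} speaks of characteristics taken during the survey, so the timing of the socioeconomic items is unclear, and complete-case analysis ({20c}) could drop people with missing items. Both are fair and shape the fix. Neither affects age group or sex, and {13} shows baseline data taken before installation.

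**Conclusion.** The point holds as an avoidable inefficiency, at the low end of what should be changed. Under assumed covariate effects, adjustment adds from nothing to about 4 power points, or about 2 points if only a steep age pattern is exploited. It also removes chance imbalance in these factors from the estimate. If the covariates are not prognostic, the loss is within simulation error.

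A reader might infer more than the documents support:

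- That the variables are merely tabulated. They are not, since {20b} also uses them for subgroups.
- That the trial falls short of its power because of this. It does not, since 90% is reached without covariates.
- That the Protocol shows a strong age gradient, because {9} reports that "prevalence by PCR in the study area was more than 40% in the survey designed to assess" gametocytes while {14} plans on 20%. That survey concerned children aged 7 and above and gives no comparison between ages. The gap bears on the planning prevalence and does not show an age effect.
- That defining age subgroups proves age to be prognostic. Subgroups concern variation in the intervention effect.

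**What to change.** In {20a}, before the January 2022 survey and consistent with any analysis plan, add one sentence. It should name age group (the three groups of {20b}) and sex as fixed covariates in the primary model and in the January/February qPCR model.

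Add socioeconomic quintile only if it is built from items recorded at enrolment before installation, with a category for missing values so that no participant is dropped. Report the unadjusted result beside the adjusted one, and say that the adjusted odds ratio is conditional on the covariates.

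Two consequences need a word. {20b} inherits the primary model, so it should say how the covariate that defines a subgroup is handled. {20a} places clinical malaria under the same approach but gives no expected number of cases, so it should say whether the covariates apply there.

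The cost is small. No new data are needed. The full set adds at most 8 parameters (2 for age, 1 for sex, 4 for quintile, 1 for missing), against about 1012.5 × (0.20 + 0.14) = 344 expected positives. The downside is that the odds ratio becomes conditional and that the gain may be nil.

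### Households are randomised within sub-villages, but the stated malaria and mosquito models name no sub-village term, so a small and conditional gain in precision may be lost

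*Protocol*

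**What the plan says.** Sub-village is the randomisation stratum, and the protocol says so twice. Sequence generation {16a} describes "Simple randomization within blocks of" sub-villages. Implementation {16c} has the trial statisticians generate the "allocation sequence and assign households to interventions through randomization stratified by" sub-village.

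Statistical methods {20a} gives the primary analysis as mixed effects logistic regression with a "random effect for household to account for clustering". The secondary malaria outcomes "will also be analysed following the same approach". For the entomological outcome, "Negative binomial mixed effect model will be performed for mosquito density data, with random" effect for household. Additional analyses {20b} estimates subgroup effects on malaria "prevalence at both surveys using the same methods as for the primary endpoint".

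None of these passages mentions sub-village. Section {20a} lists no fixed effects at all, so the term is left unnamed and is not explicitly excluded.

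**The concern.** A stratified design pays off in the analysis only if the model uses the strata. If malaria prevalence or vector density differs between sub-villages, a model with a household random effect alone absorbs that difference into the household variance. Two things follow.

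- If each sub-village was split into equal halves, the treatment estimate already benefits from the balance, but the reported standard error does not show it. The interval is then somewhat too wide and the test mildly conservative.
- If allocation within a sub-village was closer to a coin toss, which the wording in {16a} leaves open, chance imbalance between sub-villages also stays in the estimate.

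Precision is at stake, not validity. Neither case makes the primary test anti-conservative, and the sample size did not rely on stratification.

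**Working it through.** **Inputs.** Sample size {14} gives: "With 225 houses per arm was an assumed 4.5 residents per household (14), then if prevalence in" "the control arm is 20% the study would have 90% power to detect a relative reduction of 30% to a" prevalence of 14%, with a between-house coefficient of variation (CV) of 0.5. The significance level is not stated there; two-sided 5% is assumed. The protocol gives neither the number of sub-villages nor the share *s* of between-house variance that lies between them, so both are assumptions below.

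**Step 1: reproduce the stated power.** Variance per pair of houses (one per arm):

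V(s) = p0(1−p0)/m + p1(1−p1)/m + CV²(1−s)(p0² + p1²)

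With p0 = 0.20, p1 = 0.14, m = 4.5 and s = 0:

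- within-house part: 0.16/4.5 + 0.1204/4.5 = 0.0623
- between-house part: 0.25 × (0.04 + 0.0196) = 0.0149
- total: 0.0772

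The standard error is √(0.0772/224) = 0.01857, using 225 − 1 houses per arm. Then 0.06/0.01857 = 3.232, and power = Φ(3.232 − 1.960) = 89.8%. This matches the stated 90% with no stratum term.

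**Step 2: remove the between-sub-village share.** The interval width scales as √(V(s)/V(0)). The household equivalent is 450 × (1 − V(s)/V(0)).

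| Assumed share s | V(s) | Power | Interval narrower by | Households |
|---|---|---|---|---|
| 0 | 0.0772 | 89.8% | 0 | 0 |
| 10% | 0.0757 | 90.4% | 1.0% | 9 |
| 25% | 0.0735 | 91.2% | 2.4% | 22 |
| 50% | 0.0698 | 92.5% | 5.0% | 43 |
| 100% | 0.0623 | 94.9% | – | – |

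The between-house part is 0.0149/0.0772 = 19.3% of the total, so the gain cannot exceed about 5 points.

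**Step 3: simulate the stated model.** The formula is for a difference in proportions, so the mixed logistic model was simulated with and without sub-village fixed effects (2,000 runs per cell, Wald test). Assumed: 15 sub-villages of 30 houses, 4 or 5 residents per house, and a total between-house SD of 0.615 on the logit scale (CV about 0.48 at 20% and 0.53 at 14%).

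| Share s | Equal halves: without v with | Coin toss: without v with |
|---|---|---|
| 0 | 91.2 v 91.9 | 90.8 v 90.5 |
| 10% | 91.5 v 92.2 | 90.8 v 91.1 |
| 25% | 91.5 v 92.6 | 91.1 v 91.8 |
| 50% | 91.5 v 93.0 | 91.3 v 93.5 |

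The standard error of each paired difference is 0.2 to 0.4 points. At shares of 10%, 25% and 50% the gains are 0.4, 0.7 and 2.1 points with coin-toss allocation, and 0.7, 1.1 and 1.5 points with equal halves (table entries are rounded, so a difference can be off by 0.1). With equal halves, 0.7 points appear even when sub-villages do not differ. The net gain there is therefore 0, 0.4 and 0.8 points.

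A smaller simulation (12 sub-villages, 400 runs per setting, Monte Carlo SE about 1.5 points) also favoured the term. Under the null, with equal halves and s = 50%, the household-only model reported a mean standard error of 0.132 against an empirical SD of 0.123. With the term, the figures were 0.122 and 0.123.

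**Step 4: false positives.** In 1,500 null runs per setting (shares 25% and 50%), the model without the term rejected 4.1% to 5.1% and the model with 15 fixed effects 4.5% to 6.3% (Monte Carlo SE about 0.6 points).

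**Not computed.** The mosquito model cannot be sized, because the protocol gives no variance for vector density.

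**The case against.** The strongest reply is that this is a detail for the analysis plan. The protocol refers to such a plan, and {20a} is plainly not a full model specification: it does not name the treatment term either. That stands as a limit on the finding, which applies only to the models as the protocol describes them. It does not dispose of the point. For each malaria and mosquito outcome, {20a} states the model family and random effect, and a reader following it would leave the stratum out.

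The second reply is that little is lost. The test is valid, the planned power is met, and the gains from the formula exceed those from simulating the stated model. This also stands, and it is why the point is minor. Every non-zero gain rests on an assumed share and, in the simulations, an assumed number of strata.

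Third, the remedy has its own cost: many fixed effects may push the Wald test slightly above 5%, and the random-intercept alternative was not simulated. That is a reason to choose the form of the term by the number and size of the strata. It is not a reason to leave the stratum out.

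Finally, the protocol does not say that sub-villages were split unequally. Trial design {8} gives equal allocation overall, and {16a} can be read either way within a sub-village. The chance-imbalance argument therefore stays conditional.

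**Conclusion.** The concern holds, as a minor one. The randomisation uses sub-village and the stated malaria, mosquito and subgroup models do not. There is no evidence of bias, inflated type I error or a failed power calculation. On the protocol's sample-size inputs, two-sided 5% and assumed shares of 10% to 50%, the formula gives a gain of about 0.5 to 2.7 points of power. Simulating the stated model gives 0.4 to 2.1 points with coin-toss allocation and a net 0 to 0.8 points with equal halves. If sub-villages do not differ, there is nothing to gain. Confidence is medium, because the share, the number of strata and the contents of the analysis plan are unknown.

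**What to change.** State in {20a} that sub-village, as the randomisation stratum, enters the primary logistic model, the secondary prevalence models and the negative binomial mosquito model. The subgroup analyses in {20b} then inherit it. Use a fixed effect if sub-villages are few and large. If they are many or small, use a random intercept or merge them within the three villages. Report the model without the term as a sensitivity analysis. If the analysis plan already does this, one sentence in {20a} is enough.

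The change is wording only and needs no new data. The one downside is the extra parameters, with the possible slight excess of null rejections seen with 15 fixed effects.
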